### **Major hemorrhage:**

An independent adjudication committee of three hematologists will review all details of hemorrhagic events in a blinded manner to determine whether event met criteria for major hemorrhage. Any disagreements will be settled by majority consensus.

## **12. DATA REPORTING / REGULATORY REQUIREMENTS**

Adverse event lists, guidelines, and instructions for AE reporting can be found in Section 7.0 (Adverse Events: List and Reporting Requirements).

### **12.1 Data Reporting**

#### **12.1.1 Method**

The QACT will collect, manage, and perform quality checks on the data for this study.

#### **12.1.2 Responsibility for Data Submission**

Investigative sites within DF/HCC or DF/PCC are responsible for submitting data and/or data forms to the QACT according to the schedule set by the QACT.

### **12.2 Data Safety Monitoring**

The DF/HCC Data and Safety Monitoring Board (DSMB) will review and monitor study progress, toxicity, safety and other data from this study. The board is chaired by a medical oncologist from outside of DF/HCC and has external and internal representation. Information that raises any questions about participant safety or protocol performance will be addressed by the Overall PI, statistician and study team. Should any major concerns arise, the DSMB will offer recommendations regarding whether or not to suspend the study.

The DSMB will meet twice a year to review accrual, toxicity, response and reporting information. Information to be provided to the DSMB may include: participant accrual; treatment regimen information; adverse events and serious adverse events reported by category; summary of any deaths on study; audit results; and a summary provided by the study team. Other information (e.g. scans, laboratory values) will be provided upon request.

### **12.3 Multicenter Guidelines**

This protocol will adhere to the policies and requirements of the DF/HCC Multi-Center Data and Safety Monitoring Plan. The specific responsibilities of the Overall PI, Coordinating Center, and Participating Institutions and the procedures for auditing are presented in Appendix B.

- The Overall PI/Coordinating Center is responsible for distributing all IND Action Letters or Safety Reports to all participating institutions for submission to their individual IRBs for action as required.

- Mechanisms will be in place to ensure quality assurance, protocol compliance, and adverse event reporting at each site.
- Except in very unusual circumstances, each participating institution will order the study agent(s) directly from supplier. A participating site may order the agent(s) only after the initial IRB approval for the site has been forwarded to the Coordinating Center.

#### **12.4 Collaborative Agreements Language:**

N/A

### **13. STATISTICAL CONSIDERATIONS**

#### **13.1 Study Design/Endpoints**

The primary aim of randomized phase II trial is to estimate the cumulative incidence of VTE and major hemorrhage in hospitalized cancer patients receiving standard dose or weight adjusted enoxaparin.

#### **13.2 Sample Size, Accrual Rate and Study Duration**

The documented incidence of VTE in cancer patients in randomized clinical trials ranges considerably (3-17%) on pharmacologic thromboprophylaxis at standard prophylactic dosing.[8] With the additional incorporation of tumor-specific thrombotic risk assessment, we anticipate the incidence of VTE for high risk cancer patients receiving fixed standard dose enoxaparin will be greater than 10%, especially with inclusion of protocol-mandated lower extremity ultrasounds.

We plan to enroll a total of 50 high risk cancer patients between Beth Israel Deaconess Medical Center and Cleveland Clinic Foundation, of which 25 will be randomized to standard dose enoxaparin. Assuming a cumulative incidence of thrombosis at day 17 is 12% (90% binomial confidence interval 3.3 to 28.2%), While we anticipate an increased risk of major hemorrhage observed in cancer patients compared to that of general medical patients, we expect these events to be rare. Point estimates of hemorrhage endpoints at Day 14 will be provided along with the 90% exact binomial confidence intervals. The point estimate will serve to inform sample size calculations for a larger phase III clinical trial.

The trial will only be open at BIDMC and Cleveland Clinic and we anticipate enrolling 3 patients per month.

Participants who receive at least one dose of treatment post-randomization will be considered evaluable for the study.

Accrual Targets				
Ethnic Category	Sex/Gender			
	Females		Males	
Hispanic or Latino	13	+	12	= 25
Not Hispanic or Latino	12	+	13	= 25
Ethnic Category: Total of all subjects	25 (A1)	+	25 (B1)	= 50 (C1)
Racial Category				
American Indian or Alaskan Native		+		=
Asian	3	+	2	= 5
Black or African American	5	+	6	= 11
Native Hawaiian or other Pacific Islander		+		=
White	17	+	17	= 34
Racial Category: Total of all subjects	25 (A2)	+	25 (B2)	= 50 (C2)
	(A1 = A2)		(B1 = B2)	
			(C1 = C2)	

### 13.3 Stratification Factors

Randomization will be stratified for hospital (BIDMC and CCF) and risk of cancer based on Khorana model: very high risk (stomach, pancreatic), high risk (lung, lymphoma, gynecologic, bladder, testicular), and standard risk (all others).

### 13.4 Interim Monitoring Plan

We plan an interim analysis for safety with the DSMB at any point the number of hemorrhages on Arm B is more than 2 greater than observed on Arm A. (We note that the arms are unblinded on day 14, so this plan does not compromise the integrity of the study.) If the true rate of hemorrhage on Arm B is 2%, the probability of observing 2 or more such events in 25 patients is 0.09. In this setting, we will also provide the DSMB with the rates of hemorrhage on Arm A, as this study will provide the best available estimate of the rate of hemorrhage with standard dosing enoxaparin. Efficacy data will also be provided, so that the DSMB can weigh benefit against risk.

There is no plan to adjust the planned enrollment if the event rates are lower than anticipated. The reason being is that the primary goal is evaluate point estimates of VTE and hemorrhage in order to plan for a larger trial rather than adequately power for the direct comparison between fixed dose enoxaparin and intermediate-dose enoxaparin in the current study.

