## **2.2 Study Agent (Enoxaparin)**

Enoxaparin is a low molecular weight heparin with antithrombotic properties approved by the Federal Drug Administration for prevention of deep vein thrombosis following abdominal or orthopedic surgery and in medical patients with restricted mobility during acute illness.

Enoxaparin administered subcutaneously achieves steady-state activity levels predicted by single-dose pharmacokinetics. After repeated subcutaneous administration of 40mg once daily,

the steady state is reached on day 2 with an average exposure ratio of 15% higher than after a single dose. Enoxaparin is primarily metabolized in the liver by desulfation and/or depolymerization to lower molecular weight species with much reduced biological potency. Renal clearance of active fragments represents about 10% of the administered dose and total renal excretion of active and non-active fragments 40% of the dose. In the elderly, the apparent clearance of enoxaparin following multiple subcutaneous doses is similar to younger subjects. A linear relationship exists between activity and creatinine clearance.

Standard dose enoxaparin for thromboprophylaxis in medical patients:

In a double blind multicenter parallel group study, enoxaparin at 20mg or 40mg once a day for 14 days was compared to placebo in medical patients with severely restricted mobility.[11] Patients were enrolled with the following diagnosis: congestive heart failure (NYHA class III or IV), acute respiratory failure or complicated chronic respiratory insufficiency, acute infection, or acute rheumatic disorder. A total of 1073 patients were treated on the study for a maximum of 14 days (median 7 days). Enoxaparin administered at 40mg once daily was associated with a significant reduction in thromboembolic events compared with placebo (5.5 vs 14.9, P<.001). The lower (20mg) dose of enoxaparin was not associated with a reduction in thromboembolic events (12.2%). Enoxaparin (40mg) was well tolerated with 6 of 360 patients suffering a major hemorrhagic event compared with 4 of 362 treated with placebo. There were 8 cases of thrombocytopenia in the placebo group and 2 in the enoxaparin (40mg) treated group. There were no significant differences in the groups for any other adverse outcomes.

Modified dose enoxaparin thromboprophylaxis in cancer patients:

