## 7.2 Expected Toxicities

### 7.2.1 Adverse Events List for enoxaparin

Enoxaparin can be associated with an increased risk of hemorrhage including life threatening retroperitoneal, gastrointestinal, or intracranial hemorrhages. Cases of epidural or spinal hematomas have been reported with the associated use of enoxaparin and spinal/epidural anesthesia or spinal puncture resulting in long-term or permanent paralysis. The risk of these events is higher with the use of post-operative indwelling epidural catheters or by the concomitant use of additional drugs affecting hemostasis such as NSAIDs. The rate of major bleeding episodes following enoxaparin (40mg daily) in medical patients with severely restricted mobility during

acute illness was <1%.

Thrombocytopenia can occur with the administration of enoxaparin. Moderate thrombocytopenia (platelet counts between 100,000/mm^3 and 50,000/mm^3) occurred at a rate of 1.3% in patients given enoxaparin, 1.2% in patients given heparin, and 0.7% in patients given placebo in clinical trials. Platelet counts less than 50,000/mm^3 occurred at a rate of 0.1% in patients given enoxaparin, in 0.2% of patients given heparin, and 0.4% of patients given placebo in the same trials. Thrombocytopenia of any degree should be monitored closely. Cases of heparin-induced thrombocytopenia with thrombosis have also been observed in clinical practice. Some of these cases were complicated by organ infarction, limb ischemia, or death.

Asymptomatic increases in aspartate (AST [SGOT]) and alanine (ALT [SGPT]) aminotransferase levels greater than three times the upper limit of normal of the laboratory reference range have been reported in up to 6.1% and 5.9% of patients, respectively, during treatment with enoxaparin. Similar significant increases in aminotransferase levels have also been observed in patients and healthy volunteers treated with heparin and other low molecular weight heparins. Such elevations are fully reversible and are rarely associated with increases in bilirubin.

Mild local irritation, pain, hematoma, ecchymosis, and erythema may follow subcutaneous injection of enoxaparin.

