### 13.5 Analysis of Primary Endpoints

Cumulative incidence of VTE at day 17 (in arm A) and major hemorrhage endpoints at day 14 (both arms) will be calculated along with their 90% exact binomial confidence intervals.

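### The 0.09 beside the interim safety trigger belongs to a different event; at the same 2% Arm B rate the written trigger has a probability of about 0.01

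*Combined protocol and SAP*

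**What the plan says.** Section 13.4 (Interim Monitoring Plan) plans a safety analysis with the DSMB "at any point the number of hemorrhages on Arm B is more than 2 greater than observed on Arm A". Counts are whole numbers, so the condition is an Arm B excess of at least 3, checked continuously.

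The same paragraph then takes a true Arm B hemorrhage rate of 2% and states that "the probability of observing 2 or more such events in 25 patients is 0.09". It gives no Arm A rate and no other probability. It adds that Arm A hemorrhage rates and efficacy data will go to the DSMB.

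No other section gives the trigger's probability. Section 12.2 provides for routine oversight ("The DSMB will meet twice a year to review accrual, toxicity, response and reporting information") but sets no numerical threshold.

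**The concern.** The rule and the figure differ in two ways. The rule uses the difference between arms, while the figure uses the Arm B count alone. The rule needs an excess of 3, while the figure needs a count of 2. The 0.09 therefore cannot tell the DSMB or the study team how readily a review would be called.

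The text does not show which of the two is the slip. The threshold may be as intended and the figure carried over from another rule, or the figure may reflect the intended threshold and the rule be misworded. The sentence about also supplying Arm A rates adds to the doubt, because under a difference rule the Arm A count is already part of the trigger.

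This is the only numerical trial-level safety trigger in the documents, and major hemorrhage is a primary endpoint in both arms (Sections 1.2 and 13.5).

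A smaller point: the rule counts hemorrhages without qualification, whereas the endpoint in Sections 11 and 13.5 is major hemorrhage, adjudicated by committee. If all grades counted, both event rates and the trigger probability would be higher than the figures below.

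**Working it through.** **Inputs**
- Patients per arm: 50 in total, "of which 25 will be randomized to standard dose enoxaparin" (Section 13.2), which leaves 50 − 25 = 25 on Arm B.
- Arm B rate: 2% (Section 13.4).
- Arm A rate: not stated for the rule, so a range is used. The values are 0%; 1%, the upper limit of the below-1% major bleeding rate in Section 7.2.1; 6/360 = 1.7%, from Section 2.2 ("6 of 360 patients suffering a major hemorrhagic event compared with 4 of 362 treated with placebo"); and 2%, equal to Arm B.

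**Step 1. Reproduce the plan's figure.** Let X be Binomial(25, 0.02).
- P(X = 0) = 0.98^25 = 0.6035
- P(X = 1) = 25 × 0.02 × 0.98^24 = 0.3079
- P(X ≥ 2) = 1 − 0.6035 − 0.3079 = 0.0886, which rounds to the stated 0.09.

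The figure is right for its own event.

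**Step 2. Most favourable case for the written rule.** If Arm A has no events, the trigger is simply 3 or more on Arm B.
- P(X = 2) = 300 × 0.02² × 0.98^23 = 0.0754
- P(X ≥ 3) = 0.0886 − 0.0754 = 0.0132

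Arm A events can only lower this value, so no Arm A rate brings the written rule to 0.09 at a 2% Arm B rate.

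**Step 3. The rule at any point.** Follow D = (Arm B events) − (Arm A events) patient by patient, 25 per arm, and stop when D first reaches the threshold. The probabilities are exact by recursion. Paired, alternating and random accrual orders change them only slightly. Arm B is at 2%.

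| Arm A rate | Written rule (excess ≥ 3) | Alternative (excess ≥ 2) |
|---|---|---|
| 0% | 0.013 | 0.089 |
| 1% | 0.011 | 0.077 |
| 1.7% (6/360) | 0.010 | 0.070 |
| 2% | 0.009 | 0.067 |

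Looking only once, at full enrolment, with both arms at 2%, the values are 0.0084 and 0.0577.

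**Step 4. Size of the mismatch.** 0.0886 / 0.0132 = 6.7 and 0.0886 / 0.0095 = 9.3, so about 7 to 9 times over Arm A rates of 0% to 2%. Under the written rule, the Arm B rate that gives 0.0886 is 4.3% with no Arm A events, 4.7% with Arm A at 6/360, and 4.8% with Arm A at 2%.

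**Step 5. Why the choice of threshold matters.** The raised Arm B rates here are assumptions and are not in the documents. Values are at any point; each range runs from Arm A at 2% to Arm A at 0%.

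| Assumed Arm B rate | Excess ≥ 3 | Excess ≥ 2 |
|---|---|---|
| 5% | 0.10 to 0.13 | 0.29 to 0.36 |
| 10% | 0.38 to 0.46 | 0.64 to 0.73 |

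At an assumed 10% Arm B rate, the written rule would more often than not fail to call a review, while the lower threshold would usually call one.

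**The case against.** The strongest reply is that nothing is miscalculated. The section names the event to which 0.09 belongs and never says that it is the trigger's probability. It can be read as background: even two Arm B events would be unusual at a 2% rate. The rule is unambiguous and can be carried out as written, and no sample size, error rate or primary estimate uses the 0.09. The trigger calls a review and not a stop. Twice-yearly DSMB meetings, expedited event reporting (Section 7.4) and participant-level discontinuation for hemorrhage (Sections 5.6 and 6) all run independently of it. Section 13 also appears to use hemorrhage as shorthand for the major-hemorrhage endpoint, and a 50-patient estimation study does not promise operating characteristics.

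Much of this stands. The arithmetic is sound, the 7-to-9-fold overstatement affects only a reader who attaches 0.09 to the rule, and the consequence is modest. The raised-rate table and the definition of the counted events are useful additions, but the main point does not depend on them.

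The mismatch remains. On the background reading, the rule has no stated probability at all, and the one figure in its paragraph concerns another event. The placement invites the reader to connect the two.

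**Conclusion.** The point holds: rule and figure do not describe the same event. At the plan's 2% Arm B rate the written trigger has a probability of about 0.01 (0.009 to 0.013 for Arm A between 2% and 0%), against the 0.09 printed beside it. Lowering the threshold to an excess of 2 gives 0.067 to 0.089 over the same range, and matches 0.09 only if Arm A has no events.

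These results assume 25 patients per arm, independent patients, a constant event rate within each arm, and the stated range of Arm A rates, which the plan does not supply for this rule. They count one class of event at 2%; a broader definition of hemorrhage would raise them.

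It should be fixed, but it does not threaten the trial. At 3 patients per month, accrual takes 50/3 = 16.7 months, so about three routine DSMB meetings would fall within it. The primary estimates are unaffected.

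**What to change.** In Section 13.4, make the rule and the probability refer to the same event. The choice of threshold is the sponsor's.
- If an excess of at least 3 is intended, keep the rule and replace 0.09 with about 0.01.
- If an excess of at least 2 is intended, reword the rule and quote about 0.07 (both arms at 2%) to 0.09 (no Arm A events), calculated for checking at any point.

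In either case:
- state the hemorrhage rate assumed for each arm;
- add the trigger probability at a few raised Arm B rates, labelled as assumptions;
- say whether the count is of adjudicated major hemorrhages.

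The cost is two or three sentences. Sample size, data collection and the primary analysis do not change. Only the chance of an ad hoc DSMB review depends on the threshold confirmed: with Arm B at 2%, about 0.01 under the first option or about 0.07 to 0.09 under the second.

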#### **3.2 Exclusion Criteria**

3.2.1 History of allergic reactions attributed to heparin or low molecular weight heparin

- 3.2.2 Active bleeding or otherwise considered high risk for hemorrhage (e.g. known acute gastrointestinal ulcer)
- 3.2.3 Any history of significant hemorrhage (requiring hospitalization or transfusion) within the last 6 months (excluding hemorrhage during operative procedure).
- 3.2.4 History of heparin induced thrombocytopenia
- 3.2.5 Presence of coagulopathy (PT or PTT > 1.2 x upper limit of normal)
- 3.2.6 Known diagnosis of disseminated intravascular coagulation
- 3.2.7 Currently receiving therapeutic anticoagulant therapy or dual antiplatelet therapy (eg. aspirin and clopidogrel)
- 3.2.8 Uncontrolled arterial hypertension (systolic blood pressure > 200mmHg, diastolic >110mmHg)
- 3.2.9 Active peptic ulcer disease
- 3.2.10 Bacterial endocarditis
- 3.2.11 Received any type of pharmacologic thromboprophylaxis (e.g. low molecular weight heparin or heparin) for >48 hours during current hospitalization
- 3.2.12 Known brain metastases

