## **4. REGISTRATION PROCEDURES**

### **4.1 General Guidelines for DF/HCC and DF/PCC Institutions**

Institutions will register eligible participants with the DF/HCC Quality Assurance Office for Clinical Trials (QACT) central registration system. Registrations must occur prior to the initiation of protocol therapy. Any participant not registered to the protocol before protocol therapy begins will be considered ineligible and registration will be denied.

An investigator will confirm eligibility criteria and a member of the study team will complete the QACT protocol-specific eligibility checklist.

Following registration, QACT office will perform randomization to Arm A or Arm B of enoxaparin. Randomization arm will be communicated directly through QACT to the research pharmacy at Beth Israel Deaconess Medical Center. For participants enrolled at Cleveland Clinic, a representative from the BIDMC Research Pharmacy will forward the randomization assignment to the dedicated contact at the Cleveland Clinic Research Pharmacy.

Issues that would cause treatment delays should be discussed with the Overall Principal Investigator (PI). If a participant does not receive protocol therapy following registration, the participant's registration on the study must be canceled. Notify the QACT Registrar of registration cancellations as soon as possible.

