**5.2.3 Day 14 -4, + 7 days**

Enoxaparin should be continued until either hospital discharge or day 14. After receiving the final dose of enoxaparin no additional doses of enoxaparin on study will be administered. Assessment for evidence of major hemorrhage or VTE will be recorded. After the day 14 clinical assessment, study staff will become unblinded to treatment allocation in order to appropriately schedule a bilateral lower extremity ultrasound for study subjects on Arm A (see 5.3 below). For participants who remain hospitalized, study subjects should continue with standard pharmacologic thromboprophylaxis per the discretion of the treating physician. Day 14 symptom assessment can be performed by phone.

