**5.3 Off treatment procedures (unblinding)**

Following the completion of the day 14 assessment, study staff will contact a clinical research pharmacist at BIDMC. Criteria for off treatment will be reviewed and then the study staff will be informed as to whether the participant was previously assigned to Arm A (standard enoxaparin) versus Arm B (weight-based enoxaparin). For participants randomized to Arm A, a bilateral ultrasound will be scheduled (see study calendar) to evaluate for asymptomatic deep vein thrombosis.

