9.2.1.3 Site Performing Correlative Studies: BIDMC

## 10. STUDY CALENDAR

Baseline evaluations are to be conducted within 48 hours prior to start of protocol therapy.

Event/Procedure	Screening/ Pre-treatment	Day 1	Days 2-6 a	Day 7 a,c	Days 8-13 a	Day 14	Day 17
Day Range	-2 to 0			± 1 day		-4, +7 days	± 5 days
Eligibility Assessments	X						
Informed Consent	X						
Inclusion/Exclusion Criteria	X						
Medical History	X						
ECOG Performance Status Score	X						
Concomitant medication review	X			X		X	
Randomization	X						
Administer enoxaparin		X	X	X	X	X	
Clinical Assessments							
Physical examination including vital signs, and height	X						
Clinical Prediction Score data collection	X						
Weight	X			X			
Assessment of signs and symptoms of VTE and bleeding	X			X		X	
Laboratory Tests							
Plasma storage for correlative studies	X						
Complete blood count	X d	X		X			
PT/PTT	X						
Creatinine	X	X		X			
AST/ALT	X						
Imaging							
Bilateral lower extremity ultrasound							X b

a: Study subjects will only remain on treatment while hospitalized or until day 14, whichever comes first.

b: Arm A ONLY (standard dose enoxaparin).

c: Day 7 study visit not mandatory if participant is no longer hospitalized.

d: Also record CBC from initial admission

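### Telling study staff each arm at about day 10 to 21 while stratified enrolment continues weakens allocation concealment if a restricted scheme is used, and 13.4 should not rest integrity on it

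*Combined protocol and SAP*

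**What the plan says.** **Disclosure.** Under 5.2.3, once the day 14 clinical assessment is done, "study staff will become unblinded to treatment allocation in order to appropriately schedule a bilateral lower extremity ultrasound" for Arm A. Section 5.3 gives the mechanism: staff contact a research pharmacist at BIDMC and "the study staff will be informed as to whether the participant was previously assigned to Arm A (standard enoxaparin) versus Arm B (weight-based enoxaparin". Section 5.1 says the same. The study calendar (section 10) allows the day 14 assessment from 4 days early to 7 days late, and schedules the scan at day 17 ± 5 for Arm A only.

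**Enrolment.** Section 13.2 plans 50 patients, 25 of them on standard dose, at 3 per month. Section 13.3 states: "Randomization will be stratified for hospital (BIDMC and CCF) and risk of cancer based on Khorana model", with three cancer-risk levels. QACT randomizes centrally and informs the research pharmacy (4.1). No randomization method, block size or concealment of block size is given.

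**Who enrols.** Section 4.1: "An investigator will confirm eligibility criteria and a member of the study team will complete the QACT protocol-specific eligibility checklist". Under 4.3 and 4.4 a coordinator at the lead site enters participants from other sites. One exclusion (3.2.2) reads "Active bleeding or otherwise considered high risk for hemorrhage", and 3.1.5 requires a judgement of life expectancy.

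**Interim monitoring.** Section 13.4 sends the study to the DSMB whenever Arm B hemorrhages exceed those on Arm A by more than two, and adds in parenthesis: "We note that the arms are unblinded on day 14, so this plan does not compromise the integrity of the study".

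**The concern.** Arms are released one participant at a time throughout accrual, not when enrolment closes. Stratifying has a balancing purpose only under a restricted scheme such as permuted blocks or minimization. Such schemes become partly predictable once earlier assignments in the same stratum are known. The documents do not separate the staff who receive the arms from those who screen, confirm eligibility or record events.

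A team that expects Arm B next could, without intending it, judge a frail patient to be at too high a bleeding risk. Blinded dosing and blinded adjudication cannot correct this, because it happens before randomization. It could shift the case mix in each arm. That would affect the hemorrhage and VTE estimates meant to inform phase III, the difference in counts that triggers DSMB review, and the exploratory symptomatic-VTE comparison in 13.6.1.

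**Working it through.** **The plan's own figure.** The probability in 13.4 reproduces: 1 − 0.98^25 − 25 × 0.02 × 0.98^24 = 0.0886, stated as 0.09. It does not bear on predictability, for which the documents give no figure.

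**Timing, from 13.2 and the calendar.**
- Accrual: 50 / 3 = 16.7 months.
- Patients enrolled during one participant's blinded period, with a 30.4-day month: 3 × 10/30.4 = 1.0, 3 × 14/30.4 = 1.4 and 3 × 21/30.4 = 2.1, for disclosure at day 10, 14 and 21. Nearly all enrolment therefore takes place with some earlier arms known.
- Strata: 2 hospitals × 3 risk levels = 6, so about 3/6 = 0.5 patients per month in each if they are equal.
- Chance that the previous patient's arm is released before the next patient arrives in that stratum: exp(−0.5 × 14/30.4) = 0.79 at day 14 and exp(−0.5 × 21/30.4) = 0.71 at day 21. In a busy stratum (assumed 1.5 per month) these are 0.50 and 0.35.

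**Ceiling with every earlier arm known.** For blocks of size 2m, the share of correct guesses is [m + ½(4^m / C(2m,m) − 1)] / 2m, and the share of certain allocations is 1/(m+1).
- Blocks of 2: 75% correct, 50% certain.
- Blocks of 4: 71% and 33%.
- Blocks of 6: 68% and 25%.

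**With the disclosure delay.** I simulated 1,500 trials per setting: 50 patients, Poisson accrual at 3 per month, and a guesser who knows the block size and uses only the arms already disclosed in the current block. Results for 6 equal strata:

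| Scheme (assumed) | Correct, day 14 | Certain, day 14 | Correct, day 21 to day 10 | Certain, day 21 to day 10 |
|---|---|---|---|---|
| Simple | 50% | 0% | 50% | 0% |
| Blocks of 2 | 68% | 37% | 66-70% | 32-39% |
| Blocks of 4 | 66% | 23% | 65-67% | 21-25% |
| Blocks of 6 | 64% | 16% | 63-64% | 14-16% |

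With risk levels split 15/35/50%, the overall ranges are 62-69% correct and 13-38% certain. Stratification makes prediction easier here, because slow accrual within a stratum gives time for disclosure. Blocks of 4 without strata give 59% correct at day 14, against 66% with them.

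**Sensitivity of the estimates.** One event in 25 is 4 percentage points. The 90% exact upper limit is 1 − 0.05^(1/25) = 11.3% for 0/25 and 17.6% for 1/25. This shows how much one patient matters. It does not estimate a bias.

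**The parenthesis in 13.4.** Its subject is the interim count. That count can trigger review at any time, yet on average about 1.4 participants (1.0 to 2.1) are still within their blinded period. A hemorrhage in one of them can be assigned to an arm only by someone already unblinded, and no holder of the count is named. An assessment held at day 10 also releases the arm four days before the day 14 hemorrhage time point.

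**The case against.** **Staff can predict allocations.** A reader might infer this as fact. The documents do not support it. The method is unstated, randomization is central, and simple randomization would give no predictability. Undisclosed varying blocks, or minimization with a random element, would also make guessing harder. A planned 25 per arm with stratification suggests a restricted scheme but does not prove one.

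**13.4 makes a false statement about concealment.** It does not address concealment. It says that counting hemorrhages by arm adds no unblinding beyond what already occurs. What stands is narrower: the reason is incomplete even for that purpose.

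**The full-knowledge ceiling is the size of the problem.** It is not, because some arms are still undisclosed when the next patient arrives.

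**Staff could hold a patient back for a better slot.** This is barely feasible. Section 3.2.11 excludes patients with more than 48 hours of prophylaxis in the current admission, and screening spans two days. The chance that another patient enters the same stratum within 2 days is 1 − exp(−0.5 × 2/30.4) = 3%, or 1 − exp(−1.5 × 2/30.4) = 9% in a busy one. Passing a patient over remains possible.

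**Bleeding assessment is unblinded.** It is largely protected. The arm is released after the day 14 assessment, hemorrhages are adjudicated blinded by three hematologists (section 11), and the exploratory comparison uses data collected before unblinding.

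**The primary results are single-arm estimates, and no shift is demonstrated.** Both are true, and they limit the weight of the point. A selected case mix can nevertheless move a single-arm estimate without any between-arm test.

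**Conclusion.** The point stands as a conditional risk created by a stated procedure. Arms reach study staff at about day 10 to 21 throughout some 17 months of stratified enrolment, with no separation from those who decide eligibility. If allocation uses permuted blocks of 2 to 6 within 6 equal strata, and staff know or infer the block size, about 63-70% of allocations could be guessed correctly and 14-39% would be certain. Under simple randomization the figures are 50% and none. Minimization was not calculated.

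The documents do not show that any estimate is biased or by how much; they support only that case mix could shift by arm. In 13.4, day 14 unblinding is not a sound safeguard even for the interim count, because some participants are still blinded when the trigger can apply. This is an inexpensive improvement to a small estimation trial, not a flaw that invalidates it.

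**What to change.** - **5.1, 5.2.3 and 5.3:** have the research pharmacist, who is already unblinded (8.1.7), send the Arm A ultrasound request to the scheduler or vascular laboratory, or to existing staff with no part in screening or event recording. Do not give arm assignments to recruiting staff until enrolment closes.
- **13.3:** state the randomization method. Have QACT use randomly varying block sizes that are not disclosed to the sites.
- **13.4:** have QACT or the statistician hold the arm-level hemorrhage count, and delete the parenthesis.

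The cost is protocol wording and one extra step in booking the scan, with no added visits. At a small site, finding someone outside screening and event recording may be awkward, so direct routing to the scheduler or laboratory is the simpler option. Staff who follow participants may still infer some arms from who is scanned at day 17 ± 5 (about day 12 to 22), so the exposure is reduced and not removed. Undisclosed varying block sizes therefore matter as much as the rerouting.
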